4.1. Conventions for Imputing Partially Missing and Missing Dates

Partially missing and missing dates will be imputed using the following rules when used for calculating day intervals (actual data will be presented in the listings).

For **start** dates, the following rules will be used:

- Missing day and month/year present: if the month and year are the same as the month and year of the first injection then impute with the date of the first injection; otherwise, impute with the first day of the month
- Missing day and month, and year present: if the year is the same as the year of the first injection then impute with the date of the first injection; otherwise, impute with the first day of the year
- If missing date, then no imputation

For **end** dates, the following rules will be used:

- Missing day and month/year present: if the month and year are the same as the month and year of the first injection then impute with the date of the first injection; otherwise, impute with the last day of the month
- Missing day and month, and year present: if the year is the same as the year of the first injection then impute with the date of the first injection; otherwise, impute with the last day of the year
- If missing date, then no imputation

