1.5.1. Potential Risks

1.5.1.1. Potential Risks Related to the Test Product

Risks of a Single Intravitreal Injection of Ocriplasmin 0.125mg in Subjects with VMT (Symptomatic VMA)

As of 16-Apr-2016, it was estimated that 1638 eyes received an intravitreal injection of ocriplasmin (any dose) and 416 eyes received a placebo / sham injection in clinical studies.

The AEs observed after a single intravitreal injection of ocriplasmin 0.125mg in subjects with VMT (symptomatic VMA) mostly occurred within the first week after the injection. The majority of these AEs were non-serious, mild to moderate in intensity and resolved within 2 to 3 weeks without treatment. The most commonly reported AEs were vitreous floaters, eye pain, photopsia and chromatopsia, as well as conjunctival haemorrhage resulting from the injection procedure. Visual symptoms perceived in the contralateral eye or bilaterally have also been reported (such as floaters, flashes).

With data from the paediatric study TG-MV-009 excluded (16 eyes treated with ocriplasmin and 8 eyes treated with placebo), 435 serious adverse events (SAEs) have been reported in total in clinical trials; 336 of which were reported for subjects treated with ocriplasmin and 99 of which were reported for subjects treated with sham or placebo. The most frequently reported SAEs were macular hole (108 occurrences; 24.8%), retinal detachment (26 occurrences; 6.0%), visual acuity reduced (16 occurrences; 3.7%) and vitreous adhesions (14 occurrences; 3.2%). Cumulatively, 15 SAEs with a fatal outcome were reported, all of which were assessed to be unrelated to ocriplasmin.

Please refer to the current IB / the US Package Insert (USPI) / the European Summary of Product Characteristics (SmPC) for more detailed information on the risks associated with a single intravitreal injection of ocriplasmin in subjects with VMT (symptomatic VMA).

Risks of Multiple Injections in Subjects with Diabetic Retinopathy

During the clinical development programme supporting the indication of VMT (symptomatic VMA), there were a limited number of subjects who received 2 or 3 injections of ocriplasmin 0.125mg as well as a limited number of subjects with DR who were treated with ocriplasmin (0.025mg, 0.075mg, 0.125mg or 0.175mg). Overall, the risks observed in subjects with DR or after repeat injections did not seem to differ from those observed in the population included in the Phase 2 and Phase 3 studies (refer also to [Section 1.3.2](#)).

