9.6.2. Other Safety Analyses

Adverse Events

AEs (ocular, in the study and the non-study eye, and non-ocular) will be coded using the Medical Dictionary for Regulatory Activities (MedDRA). Summaries of AEs will use the system organ class (SOC) and preferred term (PT) codes, as appropriate.

AEs will be summarised by treatment arm, SOC and PT. Both the number and percentage of subjects who experience the event and the number of events will be summarised.

TEAEs, study drug-related AEs, AEs leading to withdrawal from the study and SAEs will be summarised in a similar manner. AEs will also be tabulated by maximum severity, relationship to study treatment, and onset from study treatment.

Other Safety Assessments

Descriptive statistics will be calculated by study visit and treatment arm for slit lamp examination parameters, IOP, loss of vision in BCVA, Roth 28-hue colour vision status, SD-OCT parameters and ffERG assessments.

Concomitant Medications

Concomitant medications will be listed by subject and medication name.

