3. Conventions for Analysis and Computations

All Treated Subjects Analysis Set

A single analysis set will be used. The All Treated Subjects analysis set will include subjects who are randomized and receive the first injection of study treatment. Subjects will be assigned to the treatment they receive at the time of the first injection.

Baseline Value

Baseline value is defined as the last non-missing value prior to administration of the first injection of the study drug.

Change from Baseline

Change from Baseline is calculated as the difference between the value at a considered visit minus the Baseline value. Change from Baseline will be missing if either one of the Baseline Value or the value at the considered visit is missing.

Adverse Events

Adverse events are coded using MedDRA version 18.1.

If a subject has multiple occurrences of an AE after an injection, the subject is presented only once in the respective subject count. Events are counted each time in the event column. Ocular adverse events are those that occur in either eye. Events recorded as OU (both eyes) are counted once for the study eye and once for the non-study eye, and are counted as 2 separate ocular events.

Drug related events are events considered by the Investigator with a reasonable possibility that the study treatment caused the event or events with a missing relationship.

Where severity is missing, the adverse event will be assigned to the ‘severe’ category.

AEs will be attributed to the closest injection prior to the occurrence of the event. AEs with a start date corresponding to the date of one of the injections will be attributed to that particular injection.

Treatment Emergent Adverse Events

Treatment Emergent Adverse Events are adverse events with a start date on or post the date of the first injection, or a missing start date.

Concomittant Interventions/Anti-VEGFs

Concomittant Interventions (including Anti-VEGFs) are interventions with a start date on or post the date of the first injection, or a missing start date.

Imputation of Partially Missing Dates

The conventions for imputing partially missing dates are provided in the appendix of this document.

Age Computation

The Date of Birth (DOB) will be imputed to 01JULYYYY where YYYY correspond to the year of birth. The following SAS code will be used for calculating age.

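### SAP 4.1 checks partial start dates against the first injection only, so a day-missing adverse event in the month of injection 2 or 3 can be charged to the preceding injection

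*SAP*

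**What the plan says.** SAP 3 (Adverse Events) places each AE by its start date: "AEs will be attributed to the closest injection prior to the occurrence of the event". It adds that "AEs with a start date corresponding to the date of one of the injections will be attributed to that particular injection". The same paragraphs count subjects per AE following an injection. Treatment-emergent status depends on the first injection only.

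For partial dates, SAP 3 points to SAP 4.1 and gives no separate rule for attribution. The start-date rules in SAP 4.1 are:

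- **Day missing.** If month and year are those of the first injection, "then impute with the date of the first injection; otherwise, impute with the first day of the month".
- **Day and month missing.** "if the year is the same as the year of the first injection then impute with the date of the first injection"; otherwise 1 January of that year.
- **Date wholly missing.** "If missing date, then no imputation".

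The opening line of SAP 4.1 limits the scope: such dates "will be imputed using the following rules when used for calculating day intervals (actual data will be presented in the listings").

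Protocol 9.6.2 is one user of these dates: "AEs will also be tabulated by maximum severity, relationship to study treatment, and onset from study treatment".

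**The concern.** The rule suits a decision that depends on injection 1 alone, such as treatment-emergent status. It does not suit attribution across three injections. In the month of injection 1, an event of unknown day is taken to have followed the injection. In the month of injection 2 or 3, it is taken to have preceded it. No reason is given for the difference.

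Repeat dosing is what is new in this trial. Protocol 1.3.2 reports only 9 earlier subjects with multiple 0.125mg injections, and Protocol 3.4 singles out inflammation after a 2nd or 3rd injection for escalation to the data monitoring committee. With 48 subjects randomised (Protocol clarification note), a few moved events could change a by-injection row. SAP 3 plans no sensitivity analysis that would show it.

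A second gap concerns the end date. The rule never looks at it, so an imputed start can fall after a known end.

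**Working it through.** The plan states no figure on this point, so the check applies the two rules to the calendar.

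**Inputs**

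- Spacing (Protocol Table 7): injection to assessment visit 25-31 days, then 6-10 days to the next injection. Gap = 25 + 6 = 31 to 31 + 10 = 41 days, nominally 35.
- Onset (assumption): days 0-7 after the injection. Protocol 1.5.1.1 says AEs "mostly occurred within the first week after the injection", but for a single 0.125mg injection in subjects with vitreomacular traction. The wide alternative is onset uniform over days 0-34.
- Calendar (assumption): every date of a four-year cycle (1,461 days, 48 months) is equally likely as an injection date.

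**Step 1: which branch applies.** Dates at least 31 days apart cannot share a calendar month. Enumerating all 1,461 first-injection dates with every allowed pair of gaps (1,461 × 11 × 11 = 176,781 schedules) gave no shared month. The months of injections 2 and 3 therefore always get the 1st. That precedes the injection unless it was given on the 1st (48/1,461 = 3.3%), so in 96.7% of schedules the event goes to the preceding injection.

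Example: injections on 10 January, 14 February and 21 March 2017. An AE dated only February 2017 becomes 1 February and goes to injection 1. One dated only March 2017 becomes 1 March and goes to injection 2.

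**Step 2: share misplaced, day missing.** An AE starting d days after injection 2 or 3 is misplaced if it falls in the injection's own month and the injection was not on the 1st. If it falls in a later month, the 1st of that month lies after the injection and attribution is right.

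- Days 0-7. A month of L days has 8L − 28 same-month combinations of injection date and onset day. Over 48 months: 8 × 1,461 − 28 × 48 = 10,344. Subtract injections on the 1st: 48 × 8 = 384. Misplaced: 9,960 / (8 × 1,461) = 9,960 / 11,688 = **85.2%**.
- Days 0-34. A month of L days has L(L + 1)/2 combinations: 28 × 496 + 16 × 465 + 3 × 406 + 1 × 435 = 22,981. Subtract injections on the 1st: 1,461. Misplaced: 21,520 / (35 × 1,461) = 21,520 / 51,135 = **42.1%**.
- Injection 1: the imputed date is never before injection 1 and never after the true onset, so **0%** are misplaced.

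Direct enumeration gave the same 85.2% (35-day gaps and all gaps of 31-41 days) and 42.1% (35-day gaps).

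**Step 3: year only** (35-day gaps, onset days 0-7). After injection 2, 98.8% go to injection 1. After injection 3, 89.2% go to injection 1 and 9.6% to injection 2.

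**Step 4: end date.** With injection 1 on 10 January, an AE with start January and end 5 January is given a start of 10 January. That is after its own end and, under SAP 3, treatment-emergent. The case can arise: AEs are recorded from consent (Protocol 8.4.1), and screening is 10-17 days before Day 0 (Table 7).

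**Step 5: effect of comparing the month with every injection.** With onset on days 0-7, the error after injections 2 and 3 falls from 85.2% to 0.9% (35-day gaps) or 1.3% (31-41 days). In return, 1.9% of AEs that truly followed injection 1 or 2 move to the next injection. With onset uniform over days 0-34, that reverse error is 42.1%. For year-only dates, choosing the latest matching injection would misplace 91.4% (days 0-7) or 95.1% (days 0-34) of AEs that truly followed injection 1 or 2.

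**The case against.** The strongest counter-argument is the scope clause. SAP 4.1 imputes dates for day intervals, and attribution or the treatment-emergent test can be read as a date comparison instead. On that narrow reading the rule does not misplace anything. But the SAP then has no rule at all for placing a partial date, which also needs text. This stands as a condition on the finding.

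A reader might infer that repeat-injection events are hidden. The documents do not support that. Day-missing injection-3 events that move go to injection 2, itself a repeat injection. Repeat status is lost only for injection-2 events and most year-only dates. Every misattributed event keeps its arm and its treatment-emergent status, and still counts in the any-time principal safety analysis (Protocol 9.6.1). The listings keep the recorded date.

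A reader might also take 85% as the error rate for any partial date. It holds only under the days 0-7 assumption, and some day-missing AEs in those months did begin before the repeat injection and are placed correctly.

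Partial dates near injections are probably few. There is a phone call at 24-72 hours, visits follow at about 7 and 28 days, AEs are entered within 24 hours (Protocol 8.4.1), and missing data are queried (Protocol 12.3). The published SAP omits its table shells, so the affected tables cannot be inspected, and Protocol 9.6.2 does not say which injection anchors onset. These points limit the practical effect. They do not make the rule right.

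**Conclusion.** The concern holds, within limits. If imputed dates drive attribution, the rule has a one-way error toward the earlier injection: about 85% of day-missing AEs after injections 2 and 3 with onset on days 0-7, about 42% with onset uniform over days 0-34, and none after injection 1. The damage is confined to by-injection and time-from-injection summaries. The number of partial dates is not given, so the count of affected events is unknown and may be small.

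The missing end-date cap is a separate and narrower defect. It can turn a finished pre-injection event into a treatment-emergent one, provided imputed dates also decide treatment-emergent status. If that event were ocular and in the study eye, it would enter the principal safety count.

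**What to change.** In SAP 4.1, start dates:

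1. State that the imputed dates govern attribution to an injection.
2. When the day is missing and the month and year match any injection, impute that injection's date; otherwise use the 1st of the month.
3. Never impute a start later than a known end date; where the injection date would do so, fall back to the 1st of the month.
4. Show year-only AEs as unattributed in by-injection tables. Do not assign them to the latest matching injection.
5. Flag AEs with partial start dates in the tables that use them.

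The cost is a few lines of text and code. Because the listings keep recorded dates, a count of partial start dates in the months of injections 2 and 3 would show how much is at stake.

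The downside is the reverse error in Step 5: about 2% of injection-1 and injection-2 AEs if onset is on days 0-7, up to about 42% if it is uniform over days 0-34. In the uniform case the change redirects the error and does not reduce it. Charging doubtful events to the repeat injection is the cautious direction for repeat-dose safety, and it is how the SAP already treats injection 1.

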8.4. Recording of Adverse Events

8.4.1. Adverse Events

Adverse Events (Non-serious and Serious)

(S)AEs occurring from the time of providing consent until the end of the study (Visit 11 – Month 24 / Exit Visit) must be recorded in the subject's eCRF.

(S)AEs observed during the 1-hour post-injection assessment should be recorded by the unmasked treating investigator / designee in the unmasked AE pages of the eCRF. If such an (S)AE is ongoing after the post-injection assessment, it will be followed up in a masked manner by the masked Investigator. All other (S)AEs should be recorded by the masked Investigator / designee in the masked AE pages of the eCRF.

In order to escalate relevant TEAEs in a timely manner to the DMC (refer to [Section 3.4](#)), all (S)AEs need to be recorded in the eCRF **within 24 hours** after receipt or awareness of the information.

The (S)AE term should be reported in standard medical terminology when possible. For each (S)AE, the Investigator will assess and record the date of onset, date of resolution, intensity, causality, action taken, seriousness, outcome (if applicable), and whether or not it led to withdrawal from the study.

When possible, signs and symptoms indicating a common underlying pathology should be documented as one comprehensive event with an overall diagnosis. If a diagnosis cannot be made initially, the main signs and symptoms should be documented and updated with a diagnosis when available.

Serious Adverse Events

The unmasked treating investigator / masked Investigator shall report SAEs **immediately**, and no later than 24 hours after receipt or awareness of the information, **by completing the SAE Form in the subject's eCRF**. The SAE Form should be completed as thoroughly as possible and verified with the corresponding source documents. It is very important that the Investigator provides an assessment of the relationship to the study drug or the injection procedure at the time of the initial SAE report. The eCRF system will automatically send the information to the Sponsor for processing.

If the eCRF system cannot be used for any reason, the Investigator shall submit the completed SAE Form by email or fax to the Sponsor (email: [contact]; fax: [name]), within the same timeframe. The data should be entered in the eCRF as soon as the system becomes available again.

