8.4.1.2. Adverse Event Intensity

The unmasked treating investigator / masked Investigator shall assess and record the intensity of the (S)AE according to the following scale:

- Mild (awareness of sign or symptom, but easily tolerated)
- Moderate (discomfort sufficient to cause interference with normal activities)
- Severe (incapacitating, with inability to perform normal activities)

An AE that is assessed as 'Severe' should not be confused with an SAE. 'Severe' is part of a scale used for rating the intensity of an event. An event is defined as 'Serious' when it meets 1 of the pre-defined outcomes as described in [Section 8.3.2](#). A severe AE can be of relatively minor medical significance / non-serious (*e.g.* severe itching). Similarly, an SAE can be of mild intensity (*e.g.* mild chest pain).

For AEs that change in intensity, the start and stop date of each intensity should be recorded.

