8.4.1.4. Adverse Event Follow-Up

Non-Serious Adverse Events

The masked Investigator will follow subjects from the study who are withdrawn from the study as a result of an AE until the event has resolved, subsided, stabilised, or until the event is otherwise explained, or the subject is lost to follow-up.

Other AEs will be followed until the subject has recovered or the subject's participation in the study is complete.

Serious Adverse Events

The Sponsor or delegated Pharmacovigilance Service Provider will follow-up SAE reports to completion. Investigators are expected to provide the additional information required for complete assessment and documentation of the SAE reports in a timely manner.

When more information becomes available, the masked Investigator must update the SAE Form in the subject's eCRF. The eCRF system will automatically send the follow-up report to the Sponsor for processing.

If the eCRF system cannot be used for any reason, the Investigator shall submit the follow-up report by email or fax to the Sponsor (email: [contact]; fax: [name]), within the same timeframe. The data should be entered in the eCRF as soon as the system becomes available again.

Copies of hospital reports, autopsy reports and other documents should be provided if they are relevant to the evaluation of the SAE.

SAEs should be followed-up until the event has resolved, subsided, stabilised, or until the event is otherwise explained, or the subject is lost to follow-up.

If the Investigator learns of any SAE at any time after a subject has completed the study, and he / she considers the event to be possibly related to the study drug or the injection procedure, he / she will notify the Sponsor by emailing or by faxing (email: [contact]; fax: [name]).

Screening Failures

For screening failures, only (S)AEs related to participation at the screening visit will be followed-up as described in the sections above.

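### SAP 4.1 applies the start-date rule (set to the first-injection date) to end dates as well, so some partial end dates are imputed before a known start; a minor error confined to derived intervals

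*SAP*

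**What the plan says.** SAP 4.1 gives separate bullets for start and end dates. For an end date with only the day missing, in the same month and year as the first injection, the instruction is "impute with the date of the first injection; otherwise, impute with the last day of the month". For an end date with only the year known, in the same year as the first injection, it is "impute with the date of the first injection; otherwise, impute with the last day of the year". The start-date bullets have the same condition and the same first branch; only the fallback differs (first day of the month or year for starts, last day for ends). A wholly missing date is not imputed.

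The scope is narrow: partial dates "will be imputed using the following rules when used for calculating day intervals", while listings show the dates as recorded. Neither SAP 4.1 nor SAP section 3 says that an imputed end must not precede the start.

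The inputs exist. Under Protocol 8.4.1, for each event "the Investigator will assess and record the date of onset, date of resolution, intensity, causality" and other items. Protocol 8.4.1.2 adds: "For AEs that change in intensity, the start and stop date of each intensity should be recorded".

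**The concern.** For a start date the first-injection clause has a clear purpose: an onset of unknown day in the injection month is placed on treatment. For an end date it has no such purpose. It puts the end on the earliest on-treatment day, whereas every other partial end goes to the latest day compatible with the record. Where the start is known to be later than injection 1, the result is an impossible interval. At stake is any duration derived from an end date: of an adverse event, of one intensity period within an event, or of a concomitant treatment.

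**Working it through.** **1. The rule itself.** Let I be the date of injection 1, S a known start with S > I, and E the imputed end. When the clause applies, E = I, so E - S = I - S < 0 without exception.
- Day missing: I = 4 March, S = 6 March, end recorded as March. E = 4 March and the interval is -2 days.
- Year only: I = 10 March 2017, S = 14 April 2017, end recorded as 2017. E = 10 March and the interval is -35 days.
- Start also imputed: I = 10 March 2017, start recorded as April 2017 (set to 1 April), end recorded as 2017. E = 10 March and the interval is -22 days.
- Records that start on or before I do not become negative.

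**2. Exhaustive check.** The check takes every injection date in a 365-day year with every later start.
- Same month: 7 × (31×30/2) + 4 × (30×29/2) + (28×27/2) = 3,255 + 1,740 + 378 = 5,373 pairs. All 5,373 are reversed.
- Same year: 365×364/2 = 66,430 pairs. All 66,430 are reversed.
- With the first-injection clause removed, no pair is reversed in either set.

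**3. Reach.** By Protocol Table 7 the earliest second injection is Day 25 + 6 = Day 31, which is always in a later calendar month than Day 0. The day-missing clause can therefore affect only events after injection 1. The year-only clause also reaches events after injections 2 and 3 in the same calendar year.

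**4. How often, given a partial end.** The documents give no figure to reproduce, so this is an illustration on assumptions. Protocol 1.5.1.1 says of a single injection in VMT that events "mostly occurred within the first week after the injection" and that the majority were "mild to moderate in intensity and resolved within 2 to 3 weeks without treatment". I enumerated 731 injection-1 dates (two calendar years), injections at Days 0, 35 and 70 with equal event counts, and onset and duration uniform over whole days. The denominator is events with a known start at least 1 day after an injection and a partial end. The cells show the share with imputed end before start.

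| Missing part | After injection | Onset (days) | Duration 14–21 d | 7–21 d | 1–21 d |
|---|---|---|---|---|---|
| Day | 1 | 1–7 | 29.4% | 40.9% | 50.8% |
| Day | 1 | 1–34 | 7.8% | 13.2% | 19.1% |
| Day | 2 and 3 | either | 0% | 0% | 0% |
| Day | all three | 1–7 | 9.8% | 13.6% | 16.9% |
| Day | all three | 1–34 | 2.6% | 4.4% | 6.4% |
| Day and month | 1 | 1–7 | 94.1% | 95.1% | 95.9% |
| Day and month | 1 | 1–34 | 90.4% | 91.4% | 92.2% |
| Day and month | 2 and 3 | 1–7 | 79.8% | 80.7% | 81.5% |
| Day and month | 2 and 3 | 1–34 | 76.1% | 77.0% | 77.8% |
| Day and month | all three | 1–34 | 80.8% | 81.8% | 82.6% |

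In the last row the median negative interval is -48 days and the worst is -(70 + 34) = -104 days. A later onset in the same year would give a larger negative value.

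**5. After the fix.** The share is 0% in every row. The last-day rule overstates duration by 14.7 days on average for day-missing ends, and by about (365 - 1)/2 = 182 days for year-only ends, with a maximum of 364.

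**The case against.** The strongest objection is that no consequence is shown. The imputation serves day intervals only. SAP section 3 defines treatment-emergent events by start date and attributes events to an injection by their occurrence. Protocol 9.6.2 tabulates onset from treatment, which uses starts. No duration table is described, and the mock tables are not in the abbreviated SAP. All of this stands and limits the impact. It does not make the rule right: the SAP wrote end-date rules for interval calculations, and any interval they feed can be impossible.

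Partial ends should also be rare. There were 48 subjects, events are entered within 24 hours of awareness, calls and visits follow each injection closely, and unclear data are queried. A year-only end beside an exact start is the least likely case. This stands too. A reader might infer from the shares near 90% that most durations are wrong, but those shares are conditional on a year-only end, whose frequency the documents do not give.

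A reader might also infer that the safety counts or the primary result are biased. The documents do not support this, because none of them depends on an end date.

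Finally, the repair has a price. For year-only ends the present rule has a mean absolute error in the end date of about 29 to 142 days across the scenarios in the working, against about 182 days after the change. The fix removes impossible values but does not make year-only durations accurate.

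**Conclusion.** The point holds as a minor error in the text. A day-missing end in the month of injection 1, or a year-only end in its year, is always imputed before any known start later than the day of injection 1. The same happens when the start is itself imputed to a later month of that year and the end is year-only. This follows from the wording and needs no assumption.

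How often it happens does rest on assumptions. For day-missing ends pooled over three injections the share is about 3% to 17%; for year-only ends it is much higher, but such records should be rare. The number of records is unknown, and whether a table not shown uses an end date cannot be judged.

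**What to change.** In both end-date bullets of SAP 4.1, delete the first-injection clause, impute the last day of the recorded month or year (as the SAP already does for every other month and year), and add that an imputed end may never precede the start. If any duration has already been derived, check it for negative values and derive it again.

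The cost is two bullets and the matching change in the derivation program. The result is an upper bound, so year-only durations should be flagged as such.

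A limit at the last contact date is reasonable for some events only. Protocol 8.4.1.4 follows ordinary adverse events until recovery or the end of participation, so for these the imputed end may be limited to the last contact where that date lies within the recorded month or year. Events leading to withdrawal are followed further, and "SAEs should be followed-up until the event has resolved, subsided, stabilised, or until the event is otherwise explained", so neither should be limited in this way.
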